1.0 Study Summary

Study Title	Virtual Reality-based Rehabilitation for Children with Traumatic Brain Injuries
Study Design	Between-subjects Randomized Clinical Trial

PROTOCOL TITLE: Virtual Reality-based Rehabilitation for Children with Traumatic Brain Injuries

Primary Objective	Refine clinically-appropriate paradigms for VR childhood TBI rehabilitation research
Secondary Objective(s)	Explore feasibility, safety and preliminary efficacy of the VICT program
Research Intervention(s)/ Investigational Agent(s)	VR-based interactive cognitive training (VICT) program
IND/IDE #	N/A
Study Population	Children 7-17 years with TBI
Sample Size	Approximately 30
Study Duration for individual participants	Up to 6 months
Study Specific Abbreviations/ Definitions	TBI-Traumatic Brain Injury VR-Virtual Reality VICT-Virtual Reality-based Cognitive Training

2.0 Objectives

2.1 Describe the purpose, specific aims, or objectives.

Our primary objective is to refine clinically-appropriate paradigms for VR childhood TBI rehabilitation research. The secondary objective is to explore feasibility, safety and preliminary efficacy of the VICT program. There are two specific aims of the study.

Aim 1. Refine clinically-appropriate paradigms for VR childhood TBI rehabilitation research.

Aim 2. Explore feasibility, safety and preliminary efficacy of the VICT program.

2.2 State the hypotheses to be tested.

Since this is a preliminary exploratory study, there are no specific hypotheses to be tested.

3.0 Background

3.1 Describe the relevant prior experience and gaps in current knowledge.

The Centers for Disease Control and Prevention (CDC) classifies childhood traumatic brain injury (TBI) as the leading cause of death and acquired disability in children, with an estimated 700,000 childhood TBI cases every year in the United States.¹⁻⁴ Defined as a disruption in the normal function of a child's brain that can be caused by a bump, blow, or jolt to the head, or a penetrating head injury, childhood TBIs often result in significant impairment in cognitive functions,¹ particularly in executive functions (EFs) due to the

vulnerability of the frontal lobes, especially in moderate to severe TBIs.⁵⁻⁷ EF involves a set of core cognitive capacities for self-controlled discipline, creativity, and flexibility.^{8, 9} This study will focus on training the three core EFs identified by cognitive science: inhibitory control (the ability to override a strong internal predisposition or external lure and do what is more appropriate or needed), working memory (the ability to hold and process information in mind as needed), and cognitive flexibility (the ability to adjust to changing environmental demands and think from different perspectives).⁸ Deficits in core EFs have profound implications for the children's daily EF⁸ and quality-of-life (QoL),¹⁰ as reflected in increased attention problems,¹¹ poorer academic performance,¹² and poorer psychosocial adjustment.¹³

However, evidence-based EF training programs specifically designed for childhood TBI are unavailable.¹⁴⁻¹⁷ As early as 2015, the CDC reported to Congress that post-TBI cognitive rehabilitation was the No. 1 unmet health care need among children with TBI and called for more innovation in this area.² Although a combination of computerized and non-computerized cognitive games has been shown effective in improving healthy children's EFs,^{9,18} four key obstacles hamper the successful implementation of such interventions in children with TBI: affordability, accessibility, adherence, and generalizability. First, implementation of broad-spectrum EF training programs is both costly for families and resource-demanding for hospitals.¹⁹ Second, existing EF training requires the presence of both therapists and patients at the hospital or clinic, which impedes accessibility for families living in remote areas, contributing to disparities in health outcomes. Third, existing EF training typically uses rudimentary paper-and-pencil tasks or artistically substandard flat-screen computer tasks, both of which are unappealing to children and adolescents who are increasingly accustomed to engaging video games available to them outside the medical setting.²⁰ This may negatively affect children's long-term rehabilitation outcomes by decreasing their willingness to participate planned training activities, especially for follow-up sessions after discharge. Fourth, partially due to the lack of variety and richness, existing EF interventions are often limited in helping children transfer learned skills to untrained life activities.⁹

3.2 Describe any relevant preliminary data.

The NCH Inpatient Rehabilitation Unit admits an average of 30 children with TBI (ICD-9 codes: 803, 850, 851, 854; no deaths, no asphyxia) annually. A five-year review of records shows that 80% (24 children/year) or more are eligible to participate in the proposed K99 study. Open-end feedback from patients and families at NCH suggested broad interest in participating in the study. Our target

sample size (N=30) is reasonable for an 18-month recruitment period. Recruitment will be monitored during the study. Additionally, we have recruited two pediatric patients with TBI from the NCH rehabilitation unit who pilot-tested the VICT program and the pre- and post-intervention measures. Both patients and their family and clinicians expressed high enthusiasm and satisfaction with the intervention.

3.3 Provide the scientific or scholarly background for, rationale for, and significance of the research based on the existing literature and how will it add to existing knowledge.

Virtual reality (VR) offers an exciting alternative EF rehabilitation strategy for three reasons. First, VR technology has the capability to offer a multitude of activities for training children with TBI in core EFs⁸ within a versatile virtual environment. Such an enriched, immersive environment has already been shown effective in promoting structural and functional recovery of the human brain.²¹ Furthermore, because all VR-based EF training occurs within a safely controlled, automated virtual environment, it takes minimal physical space and personnel resources to implement in a medical setting, reducing expenses for both the hospitals and the families. Second, VR-based EF training can be readily provided via Internet and mobile platforms. This allows EF training, especially those sessions scheduled after discharge, to be completed without requiring children to leave home. Last but not least, unlike traditional computer-based EF training, we expect VR-based EF training to exert two positive effects on children's rehabilitation²²: (1) improved adherence. VR-based EF training was found especially appealing to pediatric patients in our pilot testing, possibly due to the youth population's increasing exposure to electronic games in recent years; (2) potentially better skill transfer to real life. Although research suggests mixed results of computerized training for cognitive skills in general, we expect VR training to translate trained skills into daily EF skills and overall QoL in pediatric TBI patients because (1) EFs are domain-general cognitive skills that can be gained in one setting and transferred to another;²³ (2) studies using representative national samples of children have supported EF as domain-general skills and documented positive relations between EFs and real-life outcomes,²⁴ and (3) Our pilot test of the VICT program on two pediatric patients with TBI at NCH showed positive changes of core EF scores after intervention (although this preliminary result should be interpreted with caution given that the changes could reflect other factors, such as natural recovery).

The overall goal of the proposed research is to evaluate the feasibility, safety, and efficacy of a VR-based interactive cognitive training (VICT) program in children 7-17 years with complicated mild to

PROTOCOL TITLE: Virtual Reality-based Rehabilitation for Children with Traumatic Brain Injuries

severe TBI. The VICT program is an integrative hardware and software VR system that trains the three core EFs (inhibitory control, working memory, and cognitive flexibility)⁸ within a challenging 3D-animated rescue mission. The research is significant because it will provide important feasibility and safety data regarding implementing a novel VR-based EF rehabilitation program for children with TBI. This project is also expected to provide important data regarding the intervention's efficacy on children's core EF and daily EF (primary outcome) as well as attention problems and health-related QoL (secondary outcomes). Finally, findings from this project are expected to inform future development of a comprehensive VR-based cognitive rehabilitation program to help children with TBI achieve a healthy and productive life post-injury.

Reference List

2. Centers for Disease Control and Prevention. Report to congress on traumatic brain injury in the United States: epidemiology and rehabilitation. *Atlanta, GA: National Center for Injury Prevention and Control*. 2014:1-72.
8. Diamond A. Executive functions. *Annual Review of Psychology*. 2013;64:135-168.

4.0 Study Endpoints

4.1 Describe the primary and secondary study endpoints.

The primary study endpoint is the protocol feasibility (defined as protocol completion rate and subjective VR experience ratings) and safety (see section 4.2) of the VICT program. The second study endpoint is the preliminary efficacy of the VICT program, defined as the changes in NIH Toolbox Composite Scores before and after the intervention.

4.2 Describe any primary or secondary safety endpoints.

The primary safety endpoint is the number of adverse events. The secondary endpoint is the scores on participants' simulator sickness and exertion.

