5.0 Study Intervention/Investigational Agent

5.1 Description:

The hardware of the VICT program consists of a fully-immersive High Tech Computer (HTC) VIVE™ VR viewer (OLED display with 2160×1200 resolution, 90Hz refresh rate, and 110 degrees of field of view) powered by a high-performance laptop (Dell Alienware™ 17), a pair of surround sound headphones reworked to integrate with the VR viewer, and a wireless one-hand controller for the child to interact with the virtual environment using gestures. Furthermore, to avoid the burden of the equipment's weight on a child's head, we created a special mechanical arm to suspend the VR viewer in front of a child's eyes with adjustable headphone positions. With the system securely fixed on a wheeled workstation, a child can operate the program by reclining on the bed/wheelchair in his/her own patient room. To ensure the hygiene, each child will use a new facial pad for the viewer and a pair of new earphone covers. All parts of the equipment will be sanitized with germicidal wipes after each use.

For the software, the Windows 10-based VICT program invites children to rescue an animated character named "Lubdub" from a castle. The program consists of three challenging and child-friendly tasks that correspond to the three core EFs. During the game, children need to (1) direct a group of sentinels away from the castle gates (VR Task #1, adapted from the Spatial Stroop Task to train Inhibitory

Control), (2) successfully open a series of castle gates by replicating the cryptography sequence of items surrounding each gate in forward/backward order (VR Task #2, adapted from the Visual Working Memory Task to train Working Memory), and finally (3) rescue Lubdub inside the castle by strategically matching patterns between the Lubdub and the four surrounding guards (VR Task #3, adapted from the Wisconsin Card Sorting Task to train Cognitive Flexibility). A tutorial mode preceding the training lets children learn how to interact with VR. In the training mode, children will complete each task starting at the easiest level and gradually moving to more difficult levels as easier levels are mastered. Each training session consists of 10-30 trials per task, taking about 15 minutes in total. Children will receive visual/audio feedback to learn and optimize their performance.

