6.0 Procedures Involved*

The procedure involved for the study is described in detail below:

1) Baseline assessment. All approximately 30 children will complete the NIH Toolbox Cognition Battery tests, CPT 3, Virtual Reality Assessment, and the TBI-QOL Short Form prior to the randomization sequence. Both the assessor and the child will be unaware of group assignment at this point. Additionally, data regarding baseline measurement including proportion of planned baseline measures that are completed and the duration of each assessment will be documented.

2) Intervention. Following the baseline assessment, the approximately 30 children will be randomly assigned to one of the following two groups: intervention group (VICT training) or control group (a comparable VR game without cognitive training). The random allocation sequence will be generated using a SAS-based randomization program with 1:1 allocation ratio and random block sizes of 2 and 4. Both groups will first be provided a tutorial to be familiar with the VR environment. The length of time for either intervention game will be a minimum of 15 minutes of total play. If they are in the hospital, they will play approximately 15 minutes per day during their stay. If they have already been discharged from the hospital, the length of time is a minimum of 15 minutes of total play but can be more spread across their choice of days. Trained researchers who generate the randomization sequence and implement the VR will not participate in any subsequent outcome assessment. Note that although the length of training will vary across children depending on their length of stay or if they have been discharged, this arrangement has unique advantages over a fixed length of training in that: a) it provides consistency with standard therapies children are scheduled to receive, ensuring intervention to meet children's medical needs; and b) it ensures consistent timing and sufficient retention rates for future assessment.

Additionally, AEs and SAEs will be monitored in real-time throughout the intervention. Quantitative user feedback such as sickness, fatigue, and time estimates will be measured at the end of both the first and the last VR session. The

PROTOCOL TITLE: Virtual Reality-based Rehabilitation for Children with Traumatic Brain Injuries

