semi-structured interview from the User Feedback Survey will also be conducted at the first and last VR session on children's perceived VR experience, benefits, and challenges.

3) Post-intervention assessment. At completion of intervention, all children will again complete the NIH toolbox Cognition Battery tests, the Conners CPT 3, the Virtual Reality Assessment, and the TBI-QOL Short Form with trained staff blinded to the intervention assignment. Data regarding post-intervention measurement including proportion of planned post-intervention measures that are completed and duration of each assessment will also be documented.

4) Follow-up assessment. All children will complete a follow-up assessment within approximately 6 months after intervention completion. Clinically, this gives the child and family a long enough time to identify cognitive and behavioral problems. Research staff blinded to group assignment will administer the NIH Toolbox tests, the Conners CPT 3, the Virtual Reality Assessment, and the TBI-QOL Short Form to children at this visit. Children will complete the child-PedsQL Generic Core Scales and their parents or legal guardians/representatives will complete the BRIEF2, CBCL-APS, and parent-PedsQL. Data regarding follow-up measurement including proportion of planned follow-up measures that are completed and duration of each assessment will be documented. Data regarding recruitment including number of children screened per month; number of children enrolled per month; proportion of eligible children who enroll, and treatment-specific retention rates will be documented throughout the study and aggregated at this stage.

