9.0 Study Timelines*

9.1 Describe:

- **The duration of an individual subject's participation in the study.**
 - An individual subject's participation includes up to three assessment visits (pre-intervention visit, post-intervention visit, and follow-up visit) as well as the intervention training. The assessment visits last approximately 60 minutes per visit. The intervention training will last a minimal of 15 minutes. Since part of the purpose of the study is to explore the dose effect of the intervention, we do not set an upper limit of the intervention length, which could depend on patient's preference and patient's length of stay (if inpatient). We expect the total duration of subject's participation to last up to six months (depending on how far out the subject's follow-up appointment is scheduled upon completion of intervention).
- **The duration anticipated to enroll all study subjects.**
 - Approximately 24 months
- **The estimated date for the investigators to complete this study (complete primary analyses)**
 - August 31, 2021

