Researchers from NCH Center for Injury Research and Policy will work with colleagues throughout various departments/units across the hospital (Inpatient Rehab Unit, Neurosurgery Inpatient Unit, etc.) to identify and approach potential participants admitted to NCH. Other potential participants already discharged will be identified through trauma registry data and mailed invitation letters followed by an introduction phone call. Additional recruitment of discharged patients will be performed at follow up appointments using study flyers. Patients may also self-refer from the public domain through postings on sites such as clinicaltrials.gov (NCT03611062) and through IRB approved recruitment emails.

13.4 Describe materials that will be used to recruit subjects.

Flyers and introductory letters will be used to recruit participants. (attached). Phone, SMS, and email reminders will also be sent prior to the scheduled appointments.

13.5 Describe the amount and timing of any payments to subjects.

Children will be paid \$30 for completing Visit 1 (pre-intervention assessment), \$40 for completing intervention/training and Visit 2 (post-intervention assessment), and \$50 for completing Visit 3 (follow-up assessment). Parents will be paid \$50 for completing Visit

PROTOCOL TITLE: Virtual Reality-based Rehabilitation for Children with Traumatic Brain Injuries

3 (follow-up assessment). All incentives will be paid through Greenphire ClinCards.

Patients who come to the hospital solely for research purposes will also be provided a parking pass free of charge.

Patients/parents will sign receipts for both receiving the ClinCard and the parking pass (if applicable).

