17.0 Data Management* and Confidentiality

17.1 Describe the data analysis plan, including any statistical procedures or power analysis.

To examine the research paradigm (Aim 1), we will compute average number of children screened and enrolled per month, proportion of eligible children who enroll, treatment-specific retention rates, proportion of children who adhere to assigned condition, proportion of planned measures that are completed, and average duration of completing each measurement. To examine the feasibility and safety of the VICT program (Aim 2), the total number of AEs/SAEs, mean simulator sickness scores, and mean Borg exertion scores will be computed and compared between the intervention and control group using independent samples t-tests. Additionally, open-end feedback from children, parents, and clinicians on optimizing the VR games and best practices in protocol implementation will be synthesized and submitted to the VR development team for improvement. Finally, to explore the preliminary efficacy of the VICT program (Aim 2), difference scores from baseline to post-intervention and baseline to follow-up of the composite NIH Toolbox score, TBI-QOL, and Conners CPT 3 will be compared between the intervention group and the control group using analysis of covariance (ANCOVA) controlling for baseline scores. BRIEF2, CBCL-APS, and PedsQL (parent/child) scores at follow-up will be compared between the two groups using ANCOVA controlling for baseline scores. Cohen's d for core EFs changes will be computed as the preliminary intervention effect size. Finally, dosage effect will be evaluated within regression analyses, with dosage (0 for controls, cumulative hours of VICT training for intervention group) as the primary predictor and post-intervention NIH Toolbox scores as the outcome variable.

17.2 Describe the steps that will be taken to secure the data (e.g., training, authorization of access, password protection, encryption, physical controls, certificates of confidentiality, and separation of identifiers and data) during storage, use, and transmission.

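### Does the undefined completion rate in Section 4.1 leave the primary feasibility endpoint so open that the plan must change?

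*Combined protocol and SAP*

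**What the plan says.** Section 4.1 sets the endpoint: "The primary study endpoint is the protocol feasibility (defined as protocol completion rate and subjective VR experience ratings) and safety". It refers to Section 4.2 for safety. There the primary safety endpoint is the number of adverse events, and the secondary one is the simulator sickness and exertion scores.

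Section 17.1 does not use the term completion rate. Under Aim 1 it computes, among other items, "treatment-specific retention rates, proportion of children who adhere to assigned condition, proportion of planned measures that are completed". Under Aim 2 it compares adverse events, mean sickness scores and mean Borg exertion scores between arms as feasibility and safety results, and it plans a synthesis of open-ended feedback.

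On what there is to complete:

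- Section 9.1 says that a subject's "participation includes up to three assessment visits (pre-intervention visit, post-intervention visit, and follow-up visit) as well as the intervention training".
- Section 6.0, item 4, says: "All children will complete a follow-up assessment within approximately 6 months after intervention completion".
- On play time, Section 6.0 says: "The length of time for either intervention game will be a minimum of 15 minutes of total play". Section 9.1 agrees: "The intervention training will last a minimal of 15 minutes". Section 6.0 also describes roughly a quarter of an hour of play a day for inpatients.
- Section 6.0 documents the share of planned measures completed separately at baseline, post-intervention and follow-up. It aggregates retention by treatment at the follow-up stage.

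Section 2.2 states that there are no hypotheses to test.

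**The concern.** A primary endpoint would normally say what is counted, among whom and when. Here three planned proportions could each be called the completion rate, and they answer different questions: whether the child stayed, whether the child played as assigned, and how many instruments were filled in. A child who trains, attends the post-intervention visit and misses follow-up counts as a success on one and a failure on another. If the label is attached after the data are seen, the most favourable figure could become the headline.

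The other half of the definition raises the same doubt. The only subjective scores that Section 17.1 analyses numerically are sickness and exertion, which Section 4.2 already lists as secondary safety. The plan does not say whether these are also the experience ratings. Time estimates are collected under Section 6.0 but do not appear in Section 17.1. A child with a single session has the same first and last rating, and no handling is given.

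At stake is the descriptive figure that the trial would quote for feasibility.

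**Working it through.** The plan states no completion rate, target or power, so there is no figure to reproduce. The check asks how far the candidate readings differ, and whether the planned reporting hides the difference.

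**Inputs, from Section 6.0.** Planned measures are 4 at baseline (NIH Toolbox, CPT 3, Virtual Reality Assessment, TBI-QOL), the same 4 post-intervention, and 8 at follow-up (those 4 plus child PedsQL, BRIEF2, CBCL-APS and parent PedsQL). Total: 4 + 4 + 8 = 16. Sample size is about 30.

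**One child who trains, attends the first two visits and misses follow-up.**

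- Minimum play of 15 minutes: met.
- All three visits, or retained to follow-up: not met.
- Measures by visit, as Section 6.0 documents them: 4/4, 4/4 and 0/8.
- Measures pooled over visits: 8/16 = 50%. If the four follow-up-only scales were also given at baseline, as the baseline adjustment in Section 17.1 implies, this becomes 12/20 = 60%. Nothing in the plan calls for pooling.

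**Cohort of 30.** Assume everyone reaches the post-intervention visit and k children miss follow-up. Minimum play is 30/30. All visits is (30 − k)/30. Pooled measures is 1 − (8/16)(k/30). Follow-up measures alone is (30 − k)/30.

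| k | Minimum play | All visits, or retained to follow-up | Measures, pooled | Measures, follow-up only |
|---|---|---|---|---|
| 3 | 100% | 90% | 95% | 90% |
| 6 | 100% | 80% | 90% | 80% |
| 9 | 100% | 70% | 85% | 70% |

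The readings differ by 10 to 30 points. Exact 95% intervals are 88.4% to 100% for 30/30, 73.5% to 97.9% for 27/30, 61.4% to 92.3% for 24/30 and 50.6% to 85.3% for 21/30. The gap is therefore not always lost in sampling error.

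**What will be reported.** The third and fifth columns are both in the plan: retention by arm in Section 17.1, and follow-up measure completion in Section 6.0. With k = 6, a report that called the 100% figure the completion rate would also show 80% retained and 80% of follow-up measures done. The label can move, but the loss cannot be hidden without departing from the plan.

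**Play time.** Section 5.1 says: "Each training session consists of 10-30 trials per task, taking about 15 minutes in total". One session can thus meet the stated minimum. The daily figure for inpatients is a schedule, and Section 9.1 lets length vary with preference and stay. Stay length is not given. For assumed stays of 5, 10 or 20 days, one session is 20%, 10% or 5% of daily sessions. Dates and times of VR sessions are recorded (Section 17.4), and cumulative hours in the intervention arm enter the dosage regression in Section 17.1.

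**Ratings.** Section 17.1 places sickness and exertion under feasibility and safety together, matching the joint endpoint in Section 4.1. Interview content from the User Feedback Survey fits the planned synthesis of open-ended feedback. The survey is not in the documents, and Section 6.0 gives its quantitative items only as examples, so the full item list cannot be judged.

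**The case for a change.** The strongest case for a change is that, with no hypotheses, a descriptive feasibility figure is the main result, so its definition carries more weight than usual. Loss before a visit up to about six months later is foreseeable. One sentence would settle the matter in advance at almost no cost, from data already collected. If sickness and exertion are not the experience ratings, half of the feasibility definition has no planned numerical summary.

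Part of this stands. The plan does not name the indicator, the denominator, the time point or the rating items, and a selective headline is possible.

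Other parts are weaker. The 50% score comes from pooling measures that Section 6.0 keeps apart by visit. The idea that the protocol ends at the second visit would rest on the payment schedule in Section 13.5, which sets compensation and also pays for the third visit. The inpatient daily schedule is not presented as a completion criterion. Nor is there one evidently better definition. Requiring an NIH Toolbox composite at both later visits, for instance, would make a feasibility rate depend on the efficacy instrument and fail a child who attended everything but lacked a valid score. The differences in labelling between Sections 1.0, 2.1, 3.3 and 4.1 are editorial.

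**Conclusion.** No change to the plan follows. The gap is one of missing detail: no stated rule gives a wrong result, and each component a reader would want is already collected, with retention, adherence and measure completion all planned for reporting. Analysts can fill it sensibly. Sections 6.0 and 9.1 point to three visits and to all children, and the planned proportions can be shown side by side under their own names. A single-session child can be noted as such.

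If 3 to 9 of 30 children missed follow-up and all else were complete, the figure called the completion rate could differ by 10 to 30 points between readings, with the lower figure still in the report as retention. These counts are assumptions. The effect stops at the label, because no threshold, error rate, power or go/no-go decision uses the rate. The conclusion rests on the planned proportions being reported in full. It would be different if a decision to proceed were tied to a completion rate.
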